Pilot and Feasibility Study 2: The RISE Study also served to pilot-test some of the procedures proposed for PPG II. This study included interview, phlebotomy, and MRI-PET preoperatively and interview, phlebotomy, LP and MRI-PET at one month post-operatively. No TMS was conducted in this study. As of January 16, 2019, we have successfully completed 38 post-operative LPs and 77 MRIs for this study, without any complications or adverse effects.

B3. DESCRIPTION OF RESEARCH PROTOCOL

A. Study Design – Overview, Methods, Procedures

A.1. Brief overview of the study:

This study is based on our previous Program Project (PPG) that created the original SAGES I cohort (SAGES, Protocol: 2009P-000262). During the first PPG, we enrolled a cohort of >560 older surgical patients (SAGES I) and documented: an accelerated trajectory of long-term cognitive decline following delirium and important risk markers for delirium related to inflammation, structural disconnectivity, and impairment in global cognitive performance. These important findings have paved the way for us to move forward to extend our pathophysiologic understanding through innovative probes of brain vulnerability. This project will deepen our exploration of pathophysiologic pathways potentially contributing to delirium and its associated cognitive decline. We will examine the role of inflammation; Alzheimer's disease (AD) biomarkers (cerebrospinal fluid, CSF, and neuroimaging markers); and measures of *brain plasticity/connectivity* (transcranial magnetic stimulation and evoked potentials). These approaches were chosen based on their innovation, potential to probe vulnerability, and ability to advance our mechanistic understanding. We will also identify and validate predictors of complicated delirium, i.e., delirium associated with long-term cognitive decline. All of these studies will utilize both the original SAGES I cohort, and a new prospectively enrolled cohort, SAGES II, which will include CSF sampling obtained prior to spinal anesthesia if possible (some patients will get general anesthesia and for some with spinal anesthesia we may not get CSF).

A.2. Overall Study Design.

This observational study seeks to better describe the complex relationship of *delirium, dementia, and brain vulnerability* by exploring a different aspect of vulnerability involving two different prospective observational cohorts: Successful Aging after Elective Surgery I (SAGES I) and SAGES II.

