The SAGES I cohort will be followed with neuropsychological testing to achieve a minimum of 8 years of follow-up under a standing IRB protocol (SAGES I Protocol: 2009P-000262). From the SAGES I cohort, we will invite a subgroup (N=148) of participants who previously agreed to be contacted for other studies to undergo phlebotomy, lumbar puncture (LP), non-invasive transcranial magnetic stimulation (EEG/TMS) and magnetic resonance imaging (MRI) procedures. The SAGES I Subgroup will be called SAGES Select. SAGES Select participants who are not eligible to undergo LP to obtain CSF, will be invited instead to undergo an amyloid-PET scan. We will also continue long-term follow-up for the entire sample (N=560) over 8-12 years of follow-up under IRB protocol 2009P-000262.

SAGES II (n=460) will be newly enrolled and followed at 1, 2, 6, 12, 18, 24, and 36 months after enrollment with neuropsychological testing and will be invited to undergo the same procedures as SAGES I SELECT, with the exception that CSF will be collected prior to spinal anesthesia if possible (rather than a separate LP procedure). SAGES II participants for whom we could not get CSF at anesthesia induction will be invited to undergo an amyloid-PET scan after the one month follow-up visit. The 5 interlinked projects utilize these cohorts as described in Table 4 and below.

Table 4: Field Core Samples for the delirium P01 Renewal Project								
Cohorts	New for	Sample Size	Projects	Purpose				
	Renewal?							
	SA	GES I Cohorts						
Total SAGES I (dementia-free) sample	No	560	1, 4	Continued follow-up (2 waves, minimum				
				5 & 8 yrs post-op), prediction of LICD				
				(Protocol: 2009P-000262)				
SAGES I Select nested cohort (probability	Yes	148	ALL	CSF (or amyloid-PET) AD,				
sampling based on frequency matching)		(subset of 560)		Inflammatory, MRI, IMS/EEG				
				biomarkers of delirium (obtained ~4 yrs				
				after index admission) & LTCD (8 yrs				
				post-op)				
	SA	GES II Cohorts						
Total SAGES II Sample (MCI enriched-	Yes	460	1,2,4	Prediction of delirium and 18-36 mo				
15%)				CD—CSF AD(or amyloid-PET) &				
				inflammatory biomarkers				
SAGES II Neuroimaging and	Yes	180	3,4,5	MRI and TMS/EEG biomarkers of				
Neurophysiology Cohort (MCI enriched-		(subset of 460)		delirium, &18-36 mo CD				
25%)								
Table Abbreviations: LTCD-long term cognitive decline, 18-36 mo CD-18 to 36 month cognitive decline, MRI-magnetic resonance imaging,								

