In the prior cycle of this Program Project, a number of findings from diffusion tensor imaging and fluid biomarkers associated with inflammation were identified as predisposing to delirium. However, it is not clear whether those biomarkers might have been associated with preclinical AD pathology, vulnerable aging, or other known pathologies. Using modern magnetic resonance imaging (MRI) techniques, we have identified an "AD-Signature" of cortical atrophy and hippocampal hyperactivation as biomarkers of prodromal or preclinical AD. In addition, measures of changes in the brain that are associated with age-related cognitive decline in the absence of neurodegenerative or cerebrovascular disease can be detected as a "Vulnerable Aging-Signature" of cortical atrophy and reduced frontoparietal functional connectivity. Therefore, the overarching goal of Project 3 is to examine whether neuroimaging biomarkers of preclinical AD or vulnerable aging are predictive of delirium, delirium severity, and complicated delirium (i.e., delirium with LTCD), and to link these neuroimaging biomarkers to molecular biomarkers of pathology measured in the cerebrospinal fluid (CSF) and plasma. The Specific Aims are: 1) to determine in people with evidence of preclinical AD (i.e. patients with abnormal CSF AD biomarker levels of tau and beta-amyloid or classified as amyloid-positive in PET imaging) whether ADrelated brain atrophy or network dysfunction are associated with delirium, delirium severity, or LTCD; 2) to determine in people without evidence of preclinical AD (i.e. patients with normal AD biomarkers) whether vulnerable aging-related brain atrophy or network dysfunction are associated with delirium. delirium severity, or LTCD; and 3) to investigate whether longitudinal cortical atrophy (measured preoperatively and one year after surgery) due to preclinical AD or vulnerable aging is associated with postoperative LTCD or complicated delirium. To test these hypotheses, we will leverage the existing SAGES I cohort (N=560 total, n=126 with longitudinal MRI), augmented by new CSF (or PET) and MRI data collected in 148 SAGES I probability sampled patients (SAGES I SELECT) (74 with delirium, 74 without) about four years after their surgery, and a new SAGES II cohort (N=460), of which 180 patients will have both CSF (or PET) and MRI collected pre-operatively. The long-term objective of this Project is to improve the pathophysiological understanding of brain vulnerability to delirium in order to inform prevention strategies and, ultimately, pathophysiological-based treatments.

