A.4.8. Cerebrospinal fluid (CSF, up to n=460 entire SAGES II cohort): CSF collection will occur during spinal anesthesia for elective surgery. The procedure will be performed by the assigned anesthesia team led by experienced anesthesiologists in the operating room under standard monitoring, immediately before the planned operation. Using standard sterile technique and local anesthesia to the skin, the dural sac will be entered with an appropriately chosen Sprotte, Whitacre or Quincke needle 25-22G by the anesthesia team, under supervision of Drs. [name] (BWH), [name] (BWH-Faulkner), or [name] (BIDMC). After confirming intrathecal placement and adequate CSF flow, 2.0 ml of CSF will be collected; this amount is limited by feasibility and safety concerns of the anesthesiologists but is sufficient to accomplish the aims. Next, the anesthesiology team will inject local anesthetic for the surgical procedure through the same needle as per usual care. CSF will be centrifuged and managed in the same way as outlined above for the SAGES I SELECT cohort.

A.4.8.1. SAGES II subgroup participants for whom we could not collect CSF will be offered PET scans and using the same procedure as outlined above for the SAGES I SELECT subgroup

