A.4.9. Hospital assessments: The purpose of the hospital assessment is to monitor daily for development of delirium and to assess precipitating factors. We anticipate that all patients in the surgical group will be hospitalized. Automatic systems will be in place to notify the principal investigator immediately whenever an enrolled study patient is admitted to the BIDMC or BWH. Upon admission, the patient will be seen by the study team in the hospital (in-person or remotely via telephone or videoconference using an IRB approved platform like zoom or Starleaf), and will undergo daily 10-15 minute interviews including a cognitive screen, digit span test, CAM, DSI, MDAS ratings, and new delirium severity measures. Precipitating factors (e.g., infections, immobilization, surgical procedures, post-surgical complications) will be assessed by interview and review of the medical record using standardized, validated methods applied in our previous studies. The initial hospitalization during the study period will be considered the index hospitalization. The timing of follow-up will begin from the point of discharge. For study purposes readmission within 24 hours is considered a continuation of the hospital stay. Our study team is highly experienced in conducting such interviews in hospitalized persons, which will assist in assuring retention, as well as avoiding any interference with ongoing

medical care. If a patient is discharged on the day of surgery, we will conduct the POD 1 and/or POD 2 hospital interview in patient's discharge location or on the phone.

A.4.10. Post-hospitalization follow-up assessments: Several types of follow-up assessments will be conducted, as detailed below. These are all timed in relationship to the discharge date of the index hospitalization. Intercurrent illnesses and re-hospitalizations will be assessed at each follow-up time-point. If patients are hospitalized at the time of a scheduled follow-up assessment, we will wait for one month from hospital discharge to complete the follow-up assessment, to minimize the effects of acute illness on cognitive functioning. Some attrition is anticipated at each follow-up time point (due to mortality and losses to follow-up in this older population). These attrition rates are accounted for in all power calculations below.

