Aim 1 Analysis: For this aim, we will restrict the sample to only those subjects who have abnormal CSF or PET AD biomarkers. For H1a, we will use 2 GLM models, one for delirium incidence (log link), and one for delirium severity (identity link). The independent variables for these models are the variables from domain 2 (AD cortical thickness, memory network connectivity, hippocampal hyperactivity). Included in these GLM models are also potential confounders of demographic and baseline clinical variables. The estimated coefficients and 95% confidence intervals will allow us to assess the independent adjusted effects of this domain on delirium outcomes in this cohort of patients with abnormal preclinical AD biomarkers. We will estimate goodness-of-fit of these models by checking model residuals, estimates of the area under the ROC curve, and adjusted model R² values. For H1b, the four variables from domain 2 will be treated as independent variables in a Generalized Linear Mixed model with identity link, and the dependent variables in this model will be the longitudinal GCP values. In this model, delirium status, and the interaction between GCP and delirium status are also included. This model allows the estimation of the association (slope) between domain 2 variables, and GCP-based long term cognitive decline modified by delirium status. For H1c, we will report the correlation matrix using the nonparametric Spearman correlation coefficients for pairwise correlation among the variables of domains 2 and 4 (A β , p-tau, t-tau, NFL).

Aim 2 Analysis and Statistical Power: For this aim, we will restrict the sample to only those subjects who have normal CSF or PET AD biomarkers. The statistical approach for H2a and H2b is the same as described for Aim 1 but the independent variables for these models are the variables from domain 4 (vulnerable aging cortical thickness, frontoparietal functional and structural connectivity). For H2c, we will report the correlation matrix using the nonparametric Spearman correlation coefficients for pairwise correlation among domain 4 variables and the inflammatory biomarker variables found in Project 2.

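### SAGES II amyloid PET is scheduled after the delirium outcome but counted as pre-operative in Project 3, and the sections differ on who is offered it

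*Protocol*

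**What the plan says.** **Why PET is needed.** CSF is to be drawn at spinal anesthesia, but section A.1 accepts that "some patients will get general anesthesia and for some with spinal anesthesia we may not get CSF". The expected share without CSF is not given.

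**When PET is done.** Section A.2 says that patients in the new cohort "for whom we could not get CSF at anesthesia induction will be invited to undergo an amyloid-PET scan after the one month follow-up visit". Section A.2.3, describing Project 3, says of the new cohort that "180 patients will have both CSF (or PET) and MRI collected pre-operatively". Section A.4.8.1 gives no timing.

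**When delirium is assessed.** Section A.4.9 states: "The purpose of the hospital assessment is to monitor daily for development of delirium". Of the follow-up assessments, section A.4.10 states: "These are all timed in relationship to the discharge date of the index hospitalization".

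**Who is offered PET.** Section A.2 refers to SAGES II participants without CSF. Table 4 lists amyloid PET as an alternative to CSF for the total sample of 460, and section C.1.2 discusses PET under the N=460 cohort. Section A.4.8.1 reads: "SAGES II subgroup participants for whom we could not collect CSF will be offered PET scans".

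**How the status is used.** In section B.2.3, Project 3 Aim 1, "we will restrict the sample to only those subjects who have abnormal CSF or PET AD biomarkers". Aim 2 takes those with normal status. Delirium incidence (log link) and delirium severity are outcomes in both.

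**The concern.** Project 3 presents the AD biomarker as a pre-operative characteristic that sorts patients into two samples, within which pre-operative MRI markers are related to delirium. For patients classified by PET, the sorting variable is obtained only after the outcome has occurred. They must survive, remain in the study and come for a visit of about 2 to 3 hours (section A.3.2.5). Patients classified by CSF face no such hurdle. If delirious patients are less likely to attend, the biomarker-defined samples lose them in the no-CSF group only, and that group differs by type of anesthesia.

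The disagreement over who is offered PET matters separately. Staff following A.2 and staff following A.4.8.1 could scan different patients, and Table 4 counts on CSF or PET in the whole cohort for predicting delirium.

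**Working it through.** **1. Order of events.**

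| Event | Timing | Section |
|---|---|---|
| CSF | Immediately before the operation | A.4.8 |
| MRI (subgroup) | Before hospitalization | A.4.6 |
| Index delirium assessment | Daily in hospital | A.4.9 |
| One-month visit | After discharge | A.4.10, A.4.10.2 |
| PET if no CSF | After the one-month visit | A.2 |

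Section A.2 loosely counts follow-up from enrollment, but A.4.10 ties every follow-up assessment to discharge. PET under A.2 therefore cannot be pre-operative, and A.2 and A.2.3 conflict. The reference in A.4.8.1 to the same procedure as SAGES I SELECT concerns how the scan is done, not when.

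**2. The plan's own figure.** Project 3 H1a (section B.1.3) states power 0.87. Its inputs are 180 patients, 32% biomarker positive, 36% of those delirious, means 2.49 and 2.37 mm, SD 0.14 and two-sided alpha 0.05 (B.1).

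- Positive: 180 × 0.32 = 57.6, stated as 57. Delirious: 57 × 0.36 = 20.5.
- Power = Φ(0.12 / (0.14 × √(1/n₁ + 1/n₂)) − 1.96).
- With 20 against 37: 0.857 / 0.2775 = 3.09, and Φ(1.13) = 0.870. With 21 against 36: 0.877. A noncentral t gives 0.859 and 0.866.

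The stated figure reproduces, but only with all 180 patients holding a biomarker status.

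**3. Power if only CSF-classified patients are used.** The share with CSF is an assumption; the formula is the same.

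| Share of 180 with CSF | Positive | Delirious | Power |
|---|---|---|---|
| 100% | 57.6 | 20.7 | 0.88 |
| 80% | 46.1 | 16.6 | 0.80 |
| 60% | 34.6 | 12.4 | 0.68 |
| 50% | 28.8 | 10.4 | 0.60 |

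**4. How large could selective availability be?** All uptake values here are assumptions. Take 80% uptake without delirium whatever the amyloid status. Among delirious patients, take 50% if amyloid positive and 65% if negative. Let m be the share without CSF, equal in all cells, with status complete in the CSF group.

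- Within the no-CSF group, the amyloid-delirium odds ratio is multiplied by 0.50 / 0.65 = 0.77.
- Pooled over both groups, the multiplier is (1 − m + 0.50m) / (1 − m + 0.65m).
- m = 20%: 0.90 / 0.93 = 0.97. m = 40%: 0.80 / 0.86 = 0.93. m = 60%: 0.70 / 0.79 = 0.89.

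**5. Uptake that depends on delirium alone.** With 60% uptake if delirious and 80% if not, at the 28% incidence in Project 5 Aim 1, incidence among those scanned is 0.28 × 0.6 / (0.28 × 0.6 + 0.72 × 0.8) = 0.168 / 0.744 = 23%. This leaves an odds ratio unchanged. A risk p becomes p × 0.6 / (0.8 − 0.2p). That factor runs from 0.75 near p = 0 to 0.81 at p = 0.28, so a risk ratio from the log-link model would shift somewhat.

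**The case against.** Several counter-arguments have force.

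- **A reader might infer that the odds ratio is cut by nearly a quarter (0.77).** The documents do not support that. The factor applies only to patients without CSF and shrinks to 0.89-0.97 on pooling. It also needs uptake to depend on amyloid among delirious patients but not among the others; with the same proportional dependence in both groups, it is 1.
- **The analysis most exposed to this is not planned with PET.** Project 1 Aim 1 in section B.2.3 names CSF markers only. In Project 3 the exposures are MRI measures taken before hospitalization. For delirium incidence, those associations are biased only if uptake also varies with the MRI marker, or through the log link.
- **Retention may be good.** Project 5 Aim 2 assumes 5% dropout at its post-operative TMS sessions, and section B.2.1 reports over 99% completeness on nearly all important factors in SAGES I. Differential attendance is possible, not shown.
- **Missing data are addressed.** Section B.2.1 plans multiple imputation and pattern-mixture models. This stands in part: the Project 3 text restricts by biomarker status and does not describe imputing membership of the Aim 1 or Aim 2 sample. Imputation would not make the pre-operative label correct.
- **A reader might infer that A.4.8.1 bars everyone outside the subgroup from PET.** It does not say so, it sits under a heading covering up to all 460, and Table 4 and C.1.2 point to the whole cohort. What stands is that the sections are not aligned.
- **Excluding PET-classified patients from the primary models would cost power**, as step 3 of the working shows.

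**Conclusion.** Two inconsistencies stand on the text. PET cannot be both pre-operative (A.2.3) and after the one-month visit (A.2), and the PET population is described differently in A.4.8.1 and in A.2, Table 4 and C.1.2. The timing conflict has analytic weight because CSF-or-PET status decides who enters Project 3 Aims 1 and 2. For PET-classified patients that status is post-outcome and available only to those who attend, so selective availability is possible.

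The size of any bias cannot be derived from the protocol. It depends on the unstated share without CSF and on uptake. Under the assumptions above, the pooled effect on an amyloid-delirium odds ratio is a factor of about 0.97 to 0.89.

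A reader might also infer that the late scan misclassifies amyloid status. The documents give no basis for that; the concern is who gets scanned and how the result is labelled. Nor do they support a claim that Project 3's results will be materially biased.

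**What to change.** 1. In section A.2.3, correct the statement that PET is collected pre-operatively so that it agrees with A.2.
2. Reconcile A.2, Table 4, A.4.8.1 and C.1.2 to one PET population, so that Projects 1 and 3 work from the same rule.
3. Flag PET-based status as obtained after the outcome. Add a sensitivity analysis of the Project 3 delirium models restricted to patients with pre-operative status (CSF, or PET done before surgery). State its lower power: for H1a, about 0.80 if 80% of the 180 have CSF and 0.60 if 50% do, against the stated 0.87 (shares assumed).
4. Where lack of CSF is foreseeable (planned general anesthesia or an LP exclusion) and scheduling allows, offer the same scan before surgery alongside the subgroup's existing MRI and TMS visits. The RISE pilot described in section B2 included pre-operative MRI-PET.

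Items 1 to 3 cost wording and one extra analysis. Item 4 tightens pre-operative scheduling, since the carried-over criteria allow as little as 6 days before surgery (A.3.1) and the TMS session alone takes 4 to 5 hours (A.3.2.6). It will also produce an occasional unneeded scan if surgery is cancelled or the anesthetic plan changes.

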TMS/EEG-transcranial magnetic stimulation-electroencephalography, MCI-mild cognitive impairment, CSF-cerebrospinal fluid, AD-								
Alzheimer's Disease								

A.2.1 Project 1

Project 1 will investigate the inter-relationship of delirium and long-term cognitive decline (LTCD) with molecular biomarkers of AD pathology according to 3 general components of the new "ATN" (Amyloid– β [A β], Tau, Neurodegeneration) descriptive classification scheme for AD biomarkers with the following specific aims: (1) to examine the relationship between baseline cerebrospinal fluid (CSF) AD biomarkers (CSF A β_{42} , total tau [t-tau], phospho-tau tau/A β_{42} ratios, and neurofilament light [NFL]), sampled prior to spinal anesthesia, and development of post-operative delirium and cognitive decline over 18-36 months in a new cohort of 460 older persons undergoing joint replacement surgery (SAGES II); (2) to evaluate associations of history of delirium and AD biomarkers (CSF biomarkers or amyloid PET imaging, sampled near 4 year follow-up) with LTCD (over a minimum of 8 years) in a probability sample from SAGES I (N=148, SAGES I SELECT): 74 patients who developed delirium during the initial hospitalization and 74 who did not develop delirium during the initial or subsequent hospitalizations; and (3) after correlating CSF (or amyloid PET imaging) and plasma levels of novel SiMoA assays of t-tau and NFL obtained at follow-up in the SAGES I SELECT probability sample (N=148), to examine the relationship of pre-operative levels of these markers obtained from stored plasma with delirium incidence/severity and LTCD following delirium.

This project will probe whether fluid biomarkers identify patients who are more vulnerable to delirium, and are most likely to have cognitive decline following delirium. By probing the relationship of delirium and AD biomarkers, we will be well positioned to advance our mechanistic understanding and to develop more effective intervention strategies to forestall LTCD associated with delirium and AD. Moreover, this study may lay the groundwork for identification of potential plasma biomarkers for AD and related dementias (ADRD). If our hypotheses are confirmed, this study will offer compelling support for the importance of prevention of delirium to forestall the progression of cognitive decline in AD/ADRD.

A.2.2 Project 2

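### CSF and amyloid PET feed one AD-biomarker classification under rules that are not aligned, so a patient's group can depend on the test received; PET timing, population and use for tau/NFL are also inconsistent

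*Protocol*

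**What the plan says.** **Definition.** Section A.2.3 puts a patient in the preclinical AD group (Project 3 Aim 1) if they are among "patients with abnormal CSF AD biomarker levels of tau and beta-amyloid or classified as amyloid-positive in PET imaging". Aim 2 takes "people without evidence of preclinical AD (i.e. patients with normal AD biomarkers".

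**Pooling.** For Project 3 Aim 1, section B.2.3 says "we will restrict the sample to only those subjects who have abnormal CSF or PET AD biomarkers"; Aim 2 does the same with normal status. Project 1 Aim 2 in B.2.3 also takes CSF or PET biomarkers together and uses biomarker positivity as an exposure (H2b). The PET tracer is florbetapir, an amyloid tracer (A.3.2.5).

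**Who gets PET.** In SAGES I SELECT, "SAGES Select participants who are not eligible to undergo LP to obtain CSF, will be invited instead to undergo an amyloid-PET scan" (A.2). In SAGES II, CSF may be missing because of general anesthesia or because it was not obtained at spinal anesthesia (A.1). Those patients "will be invited to undergo an amyloid-PET scan after the one month follow-up visit" (A.2). A.4.8.1 is narrower: "SAGES II subgroup participants for whom we could not collect CSF will be offered PET scans".

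**When.** A.2.3 states that "180 patients will have both CSF (or PET) and MRI collected pre-operatively".

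**Tau and NFL.** A.2.1 describes Project 1 Aim 3 as starting "after correlating CSF (or amyloid PET imaging) and plasma levels of novel SiMoA assays of t-tau and NFL". B.1.3 sizes that correlation on 148 patients, with a minimum detectable r of .25.

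**The concern.** Project 3 rests on dividing patients into those with and without preclinical AD and studying each group separately. If the dividing rule differs by test, group membership partly reflects which test a patient could have.

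That is not a random matter. Hard LP exclusions include anticoagulant and antiplatelet use, stroke or intracranial bleed within 6 months, and lumbar hardware (C.1.1), and C.1.2 applies the same exclusions to SAGES II. General anesthesia also removes CSF, and the eligible operations range from joint replacement to pancreatectomy and open arterial repair. B.2.1 itself singles out anesthesia and surgery type for specific attention.

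In SAGES II there is a second layer. Delirium is observed in hospital, and PET status exists only for patients who come back after one month and accept a scan. Classification of the PET patients is therefore conditional on the post-operative course. This does not apply to SELECT, where PET replaces LP at the same assessment, about four years after surgery.

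An amyloid scan also provides no t-tau, p-tau or NFL value, so PET-only patients cannot contribute to any analysis that needs one.

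**Working it through.** **1. Classify four patient profiles under each reading.** A and T stand for amyloid and tau, + for abnormal. Assume CSF and PET agree on amyloid. The CSF phrase can be read as requiring both markers to be abnormal, or as listing markers of which either suffices.

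| Profile | CSF, both required | CSF, either suffices | PET |
|---|---|---|---|
| A+ T+ | Aim 1 | Aim 1 | Aim 1 |
| A+ T− | not Aim 1 (Aim 2, or neither) | Aim 1 | Aim 1 |
| A− T+ | not Aim 1 (Aim 2, or neither) | Aim 1 | Aim 2 |
| A− T− | Aim 2 | Aim 2 | Aim 2 |

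If both are required, the A+ T− patient is positive only by PET. If either suffices, the A− T+ patient is positive only by CSF. No reading that uses tau makes the two tests agree for every profile.

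**2. Reproduce the plan's Project 3 figure (H1a, B.1.3).** Inputs: 180 patients, 32% with abnormal CSF biomarkers (n = 57), 36% of these with delirium, means 2.49 and 2.37 mm, SD 0.14, two-sided 0.05. Group sizes are 0.36 × 57 = 20.5 and 36.5.

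Power = Φ[0.12 / (0.14 × √(1/20.5 + 1/36.5)) − 1.96] = Φ(3.11 − 1.96) = 0.874. The stated 0.87 is confirmed. It treats all 180 as classified by one CSF rule: 32% abnormal here and 68% normal for H2a, which sum to 100%. PET patients have no separate place in the calculation.

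**3. Reproduce the CSF–plasma correlation (Project 1 H3a, B.1.3).** Minimum detectable r = tanh[(1.96 + 0.842)/√(n − 3)], two-sided 5%, 80% power.

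| n with CSF | Share of 148 | Minimum detectable r |
|---|---|---|
| 148 | 100% | 0.229 |
| 128 | SELECT size first used for power (B.1.2) | 0.245 |
| 118 | 80% (assumed) | 0.255 |
| 104 | 70% (assumed) | 0.272 |
| 74 | 50% (assumed) | 0.321 |

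The stated .25 fits n = 128 better than n = 148. The number of SELECT patients with CSF is not given, so the last three rows only show how the figure moves.

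**4. Project 3 H1c.** This correlates MRI variables with Aβ, p-tau, t-tau and NFL. B.1.3 counts all 92 biomarker-positive patients (48 + 44), with r = 0.4 against a null of 0.1 and power 0.87. Power = Φ[(atanh 0.4 − atanh 0.1) × √(n − 3) − 1.96] gives 0.86 at n = 92, close to the stated value, and 0.75 at n = 70 (assumed).

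**5. Set the PET statements side by side.**
- Timing in SAGES II: A.2 puts PET after the one-month visit; A.2.3 lists it as collected before surgery. Both cannot hold.
- Population: A.2 covers all SAGES II patients without CSF, and Table 4 and C.1.2 list PET for the full cohort of 460; A.4.8.1 limits it to the subgroup.

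**The case against.** **The joint rule is an inference.** The phrase in A.2.3 sits in an overview and may simply name the markers, and the 32%/68% split in B.1.3 leaves no unplaced group. Cut-points and discordant results may be handled in an analysis plan not shown here. This stands against any firm claim that single-marker CSF patients fall in neither aim. It does not remove the mismatch, because step 1 finds one under either reading.

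**Adjustment is planned.** B.2.1 names anesthesia and surgery type, Project 1 Aim 2 adjusts for surgery type and comorbidity, and Project 3 includes baseline confounders. Aims 1 and 2 of Project 3 also relate MRI to outcome within a stratum; they do not compare strata. So bias in the within-stratum association is possible but not shown. Covariates do not, however, change which stratum a patient was put in.

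**The tau/NFL point is partly answered.** The H3a analysis in B.2.3 names CSF and plasma only, and pairwise correlations would naturally use patients with values. What remains is the PET alternative in A.2.1 and sample sizes that count everyone. Project 1 Aim 1 names CSF only in B.2.3 and is not the main target here.

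**A tempting stronger reading.** A reader might infer that Aim 1 will fall well short of 57 patients. The documents do not support this. The 32% is the rate of abnormal CSF biomarkers, not of amyloid positivity. Take, purely as assumptions, a PET share of 25% and tau abnormality in half of amyloid-positive patients, with both markers required in CSF. If 32% were amyloid positivity, Aim 1 would have 180 × (0.75 × 0.32 × 0.5 + 0.25 × 0.32) = 36 patients. If 32% is the CSF-rule rate, it would have 180 × (0.75 × 0.32 + 0.25 × 0.32/0.5) = 72. The direction reverses with the reading.

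**Conclusion.** The point holds as a matter of definition and internal consistency. AD-biomarker status in the pooled analyses (Project 3 Aims 1 and 2, Project 1 Aim 2) can depend on which test a patient received, and test type is tied to health and anesthesia. The only inputs are the wording of A.2.3, the pooling in B.2.3 and the fact that an amyloid scan gives no tau value.

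The effect on Project 3 cannot be sized or signed: the protocol gives neither the PET share nor the concordance of tau and amyloid. For H3a the loss can be expressed only as a function of n: the detectable r rises from 0.23 at 148 to 0.26 at 118 and 0.32 at 74, with the two smaller n assumed.

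The conflicts on SAGES II PET timing and population, and the use of PET for a t-tau and NFL correlation, stand without any assumption. A correction is advisable; nothing here shows that the design fails.

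**What to change.** 1. In the pooled analyses (Project 3 Aims 1 and 2, Project 1 Aim 2), state whether the CSF rule needs both markers or either one. Include modality as a covariate. Add two sensitivity analyses: CSF patients only, and all patients classified on amyloid status alone. The sponsor may choose the amyloid-only rule as primary, but that changes what Aim 1 studies and is a scientific decision.
2. Remove the PET alternative from Project 1 Aim 3 in A.2.1. Limit every tau and NFL analysis (H3a, Project 3 H1c) to patients with CSF, and restate n, detectable correlation and power on that number.
3. Describe SAGES II PET in A.2.3 as post-operative, as A.2 schedules it, and acknowledge that PET status is available only for patients who return. Reconcile A.2, Table 4 and C.1.2 with A.4.8.1 on who is offered PET.

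Cost: wording changes and a little more analysis, with no new tests. The tau/NFL analyses will show a smaller n.
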